## 9.5 Population Sets

### 9.5.1 Safety Analysis Set

The safety set will consist of all subjects who received at least 1 dose of trial vaccine and for whom any post-vaccination safety data are available. All safety data will be analyzed using the safety set, if not otherwise stated.

### 9.5.2 Immunogenicity Analysis Set

The immunogenicity set will include all subjects who received at least 1 dose of trial vaccine and for whom the baseline blood sample for immunogenicity assessment and at least 1 additional blood sample for immunogenicity assessment are available for analysis. All immunogenicity data will be analyzed using the immunogenicity set, if not otherwise stated.

### 9.5.3 Dose-determining Set

In case a dose-level has not been previously administered in Trial CV-NCOV-001, a dose-determining set (DDS) is defined and will consist of 4 additional subjects in the respective dose level and will be part of the safety set, who have either experienced Grade 3 adverse reactions or SAEs considered as related to the trial vaccine according to the Investigator at any time during the first 24 hours, or completed the 24-hour observation period without experiencing Grade 3 adverse reactions or SAEs considered as related to the trial vaccine according to the Investigator. The DDS will be used to confirm the safety on untested dose level prior to enrollment into the randomized part at the particular dose level. The minimum vaccination and safety evaluation requirements will have been met if the subject has received the planned dose of CVnCoV, has been observed for at least 24 hours following the first vaccine administration and has completed the required safety evaluation. Subjects who do not meet these requirements will be regarded as ineligible for inclusion in the DDS. Since DDS is only used to confirm safety prior to randomization, the DDS is not reported in the tables but Grade 3 adverse reactions and SAEs considered as related to the trial vaccine according to the Investigator used for the analyses are marked in the listings.

## 10.0 Conventions and Derivations

All data obtained in this trial and documented in the eCRF will be listed and summarized with sample statistics or frequency tables as appropriate. In all tables, listings and figures (TLFs), the dose groups will be reported from the lowest to the highest dose. The safety and immunogenicity analyses will be done overall and by age group and baseline serology status for SARS-CoV-2.

The statistical analyses will be reported using tables, listings, and figures (TLFs).

### 10.1 Baseline and Change from Baseline

Unless otherwise noted, baseline is defined as the last valid measurement at Visit 1: Day 1 prior to administration of the trial vaccine.

---

Change from Baseline is defined as:

Observed result at nominal time point – observed result at baseline.

## 10.2 Fold change from Baseline

Unless otherwise noted, fold change from baseline is defined as the ratio:

Post-baseline value/baseline value.

## 10.3 Missing Data

Analysis of vaccination data will be done on a valid case basis, i.e., for missing observations, no imputation for missing data, such as last observation carried forward, will be applied. For nCoV spike protein antibodies and Virus Neutralization, concentration values marked as below the cut point (CP) will be set to 0.5\*CP.

No imputation of missing values will be done for any analysis (except the imputation for missing partial dates of AEs and concomitant medication). Reasons for discontinuation from the trial or trial vaccination will be listed and summarized.

Currently no replacement of drop-out subjects is foreseen.

For unsolicited AEs, solicited AEs occurring after Day 8 and concomitant medications, some missing or partially missing variables will be imputed as follows:

For AE or concomitant medication start date:

- If start date year value is missing, the date uncertainty is too high to impute a rational date. Therefore, if year value is missing, the imputed AE start date is set to missing.
- If start date year value is before the vaccination start date year value, started before the vaccination. Therefore:
  - If month is missing, the imputed start date is set to the mid-year point (i.e., 01JULYYYY).
  - If month is not missing, the imputed start date is set to the mid-month point (i.e., 15MONYYYY).
- If start date year value is equal to the vaccination start date year value, the start date month needs to be compared against the vaccination start date month, to determine the imputation rule to apply. Therefore:
  - If month is missing, the imputed month and imputed day is the same as start of vaccination
  - If month is lower than vaccination start date month and start date day is missing, the imputed start date is set to the mid-month point (i.e. 15MONYYYY).
  - If month is equal to the vaccination start date and start date day is missing, the start day will be set to the start day of vaccination.
  - If month is greater than the vaccination start date month and start date day is missing, the imputed start date is set to the beginning of the month (i.e., 01MONYYYY).
- If start date year value is greater than the vaccination start date year value, started after vaccination. Therefore,
  - If month is missing, the imputed start date is set to the year start point (i.e., 01JANYYYY).
  - If start date month is not missing and start date day is missing, the imputed start date is set to the beginning of the month (i.e., 01MONYYYY).
- If after imputation of start and resolution date (see below) a start date is after the resolution date (for example if a missing day of a start date is set to 15 and the resolution date is before the 15th of the same month and year) then the start date will be set to the resolution date

For resolution date:

- If date of resolution is completely missing, it is assumed that it resolved at the date of the end of the trial.
- If year is present, it is assumed that it resolved on 31 December of that year (i.e., 31DECYYYY), or at the end of the trial if earlier.
- If year and month are present, it is assumed that it resolved on the last day of that month, or at the end of the trial if earlier.

No other safety variables will be imputed. In case the number of missing/partial dates for solicited local AEs, solicited systemic AEs or individual solicited AEs is higher than expected for the analysis of durations (in days), a sensitivity analysis will be conducted to assess the impact on the primary endpoint.

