### 10.5.3 Unsolicited Adverse Events

Unsolicited AEs occurring on the day of vaccination and the following 28 days will be collected. For unsolicited AEs occurring on the day of dose 2 and the booster dose the following rule will be used:

If the AE is occurring on the day of dose 2 but before vaccination the AE will be presented with AEs for dose 1, if the AE is occurring on day of dose 2 but on or after vaccination it will be presented with AEs for dose 2. If this rule cannot be applied (for example, if the start time of the AE is missing) but the AE occurred on the day of vaccination for dose 2 it will be presented with the AEs for dose 2. The same rule applies for any unsolicited AE occurring on the day of the booster dose.

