### 12.8.1 Analysis of Unsolicited and Solicited AEs

An overall summary of unsolicited AEs will be prepared for AEs occurring within 28 days after each dose, within 28 days after any dose, and all reported AEs (including those reported at more than 28 days after any dose), presenting the number and percentage of subjects with

---

- Unsolicited AEs
- related unsolicited AEs
- grade 3 (severe) unsolicited AEs
- grade 3 (severe) related unsolicited AEs
- SAEs (includes solicited AEs)
- related SAEs (includes solicited AEs)
- intercurrent medical conditions affecting immune response (includes solicited AEs)
- AESIs (includes solicited AEs)
- related AESIs (includes solicited AEs)
- medically attended AEs (includes solicited AEs)
- related medically attended AEs (includes solicited AEs)
- AEs leading to vaccine withdrawal (includes solicited AEs)
- AEs leading to withdrawal from trial (includes solicited AEs)

The overall summary will also be presented by sex (female/male) for any dose regardless of retrospective serology status at baseline.

The following summaries of AEs by SOC and PT will further be provided, separately for AEs occurring within the first 28 days after each vaccination, within the 28 days after any vaccination, and all reported AEs (including those reported at more than 28 days after any dose) if not otherwise stated:

- Occurrence of unsolicited AEs
- Occurrence of related unsolicited AEs
- Occurrence of unsolicited AEs by maximum severity (mild / moderate / severe)
- Occurrence of related unsolicited AEs by maximum severity (mild / moderate / severe)
- Occurrence of SAEs (includes solicited AEs)
- Occurrence of related SAEs (includes solicited AEs)
- Occurrence of SAEs by maximum severity (mild / moderate / severe) (includes solicited AEs)
- Occurrence of related SAEs by maximum severity (mild / moderate / severe) (includes solicited AEs)
- Occurrence of intercurrent medical conditions affecting immune response (includes solicited AEs)
- Occurrence of AESIs (includes solicited AEs)
- Occurrence of related AESIs (includes solicited AEs)
- Occurrence of medically attended AEs (includes solicited AEs)
- Occurrence of related medically attended AEs (includes solicited AEs)
- Occurrence of AEs leading to vaccine withdrawal (includes solicited AEs)
- Occurrence of AEs leading to withdrawal from trial (includes solicited AEs)
- Occurrence of AEs related to SMQs as defined in Section 10.5.9 (includes solicited AEs)

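### SAP 10.3 imputes partial AE start dates against the first vaccination only, so about half or more of day-missing AEs after dose 2 or a booster go to an earlier dose or to no 28-day window

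*SAP*

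**What the plan says.** SAP 10.3 sets the scope: "For unsolicited AEs, solicited AEs occurring after Day 8 and concomitant medications, some missing or partially missing variables will be imputed as follows". Solicited AEs in the diary period are outside it. The branches for onset in the year of first vaccination or later are:

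- Same year, later month, day missing: "If month is greater than the vaccination start date month and start date day is missing, the imputed start date is set to" the 1st of that month.
- Same year, same month: "If month is equal to the vaccination start date and start date day is missing", the day of vaccination is used.
- Same year, month missing: "If month is missing, the imputed month and imputed day is the same as start of vaccination".
- Later year, day missing: "If start date month is not missing and start date day is missing, the imputed start date is set to the beginning of the month".

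No branch mentions dose 2 or a booster. SAP 10.4 uses the first date of vaccination and the start of vaccination for the same date, and SAP 10.5.1 tests the imputed date against the first vaccination. The reference is therefore dose 1.

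The reporting is by dose. SAP 10.5 and 12.8 split AEs by any dose, dose 1, dose 2, Day 57 booster and Day 180 booster. SAP 12.8.1 tabulates them "separately for AEs occurring within the first 28 days after each vaccination". Unsolicited AEs after Days 1 and 29 are a primary endpoint (Protocol 4.2.1), and those after a booster a secondary one (Protocol 4.2.2).

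The only tie rule for dose attribution is in SAP 10.5.3. If the start time is missing "but the AE occurred on the day of vaccination for dose 2 it will be presented with the AEs for dose 2", and likewise for a booster.

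**The concern.** A rule tied to dose 1 answers one question: did the event start before or after the first vaccination? The by-dose tables ask which dose it followed, and the rule has no information on that. In the month of dose 1, a missing day is resolved to the vaccination day, so the event counts after the dose. In the month of dose 2 or a booster, the same gap is resolved to the 1st, so the event usually counts before the dose.

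Nothing downstream repairs this. The only later adjustment in SAP 10.3 moves a start date back to the resolution date, never forward to a dose. The conditional sensitivity analysis there concerns the duration of solicited AEs.

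At stake are the by-dose rates of unsolicited AEs, above all in the booster cells. These are planned at 30 subjects each, and the percentages use only boosted subjects. One subject with no other event in the window is 1/30 = 3.3 points.

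**Working it through.** The plan gives no figure for this, so there is none to reproduce.

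**Inputs.** Doses at Day 1, 29, 57 or 180 (Protocol Table 2). Window: the dose day and the following 28 days (SAP 10.5.3). Imputation as in SAP 10.3. Attribution to the latest dose on or before the imputed date, if within 28 days. Assumptions: onset uniform over days 0 to 28 after the dose, or over days 0 to 7 for early clustering.

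**Hand check, 30-day month.** With the dose on day u, an event is misplaced if it starts in the same month and u is not 1. The number of such onset days is min(29, 31 − u).

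- Days 0 to 28: the sum over u = 2 to 30 is 29 + 28 + … + 1 = 435, out of 30 × 29 = 870, or 50.0%.
- Days 0 to 7, with min(8, 31 − u): u = 2 to 23 gives 22 × 8 = 176, and u = 24 to 30 gives 7 + 6 + … + 1 = 28. The total is 204 out of 30 × 8 = 240, or 85.0%.

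**Real calendar.** The same was counted over 730 consecutive first-dose dates from 1 July 2020 (illustrative), on nominal days. Misplaced share = share with onset in the dose's month × share of those dated before the dose:

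- Days 0 to 28: 54.0% × 93.9% = 50.7%.
- Days 0 to 7: 88.5% × 96.3% = 85.2%.

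| Day-missing AE truly after | Kept (0–28) | Misplaced (0–28) | Misplaced (0–7) | Destination |
|---|---|---|---|---|
| Dose 2 | 49.3% | 50.7% | 85.2% | Dose 1 |
| Day 57 booster | 49.3% | 50.7% | 85.2% | Dose 2, rarely dose 1 |
| Day 180 booster | 49.3% | 50.7% | 85.2% | No 28-day window |

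With the visit windows of Protocol Table 1 and onset over days 0 to 28, 47.9% of day-missing dose 2 AEs go to dose 1 and 2.8% to no window.

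**Examples.** Doses on 16 November and 14 December 2020. An AE on 16 December with the day missing becomes 1 December and counts under dose 1. For the same subject with a Day 180 booster on 14 May 2021, an AE on 16 May becomes 1 May and counts in no window.

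**Month also missing.** Depending on the enrolment period assumed, 87.5% to 95.9% of dose 2 AEs go to dose 1 (onset days 0 to 28).

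**Share of all post-dose AEs.** The documents give no rate of partial dates. Assuming 1% to 5%: 0.507 × 1% to 5% is about 0.5% to 2.5%, and 0.852 × 1% to 5% is about 0.9% to 4.3%.

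**Opposite direction.** Dose 2 on 14 December has a window to 11 January. An AE on 25 January with the day missing becomes 1 January and is pulled into that window. With first doses from October 2020 to January 2021, 45% of day-missing AEs starting 29 to 60 days after dose 2 land in its window. For the Day 180 booster it is 46%.

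**Effect of using the latest dose in the month.** All day-missing AEs truly within 28 days after the last dose of the schedule are then kept with it, but only 47.7% (days 0 to 28) or 80.5% (days 0 to 7) of dose 1 AEs stay with dose 1. With equal numbers of events per dose, the share correctly assigned is:

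- Doses 1 and 2, days 0 to 28: current (100 + 49.3)/2 = 74.7%; changed (47.7 + 100)/2 = 73.9%.
- Doses 1 and 2, days 0 to 7: current (100 + 14.8)/2 = 57.4%; changed (80.5 + 100)/2 = 90.3%.
- Doses 1, 2 and Day 180 booster, days 0 to 28: current (100 + 49.3 + 49.3)/3 = 66.2%; changed (47.7 + 100 + 100)/3 = 82.6%.

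**The case against.** The case for leaving the rule alone has real parts.

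- **Few dates may be partial.** Diaries collect unsolicited AEs for 28 days after each dose, contacts are frequent and missing data are queried. This stands, and it limits the size of the problem.
- **Events do not vanish.** A dose 2 AE moved to dose 1 stays in the tables for 28 days after any dose. A Day 180 booster AE leaves all 28-day tables but stays in those of all reported AEs and in the listings. Treatment-emergent status is not harmed, and a subject with another correctly dated event still counts. This stands.
- **Any convention is biased.** Using the latest dose moves about half of day-missing dose 1 AEs to dose 2 under uniform onset, and 53% of day-missing dose 2 AEs to the booster in the Day 57 arm. This stands. The gain is clear only with early onset or for the Day 180 booster.
- **Dose attribution from the imputed date is inferred.** The SAP states its use for treatment-emergent status only. However, it offers no other date for the by-dose tables.

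Two stronger readings are tempting. A reader might infer that the error always hides dose 2 or booster effects. It does not: the rule also pulls events from beyond 28 days into a window, and a Day 57 booster event moved to dose 2 inflates dose 2. A reader might also take SAP 10.5.3 as a general principle that doubt goes to the later dose. It covers only hours of doubt on a known vaccination day, so it does not settle a month or a year of doubt.

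**Conclusion.** The point holds as a gap in the derivation. SAP 10.3 has no dose-specific rule, and the by-dose tables need one. Among day-missing AEs that truly follow dose 2 or a booster, about 50% are misplaced if onset is uniform over days 0 to 28 and about 85% if it falls in days 0 to 7. These shares apply to AEs with a missing day, not to all AEs; a reader might take them for the latter, which the documents do not support. At an assumed 1% to 5% of partial dates, about 0.5% to 4% of post-dose AEs are affected.

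Three kinds of event are dated acceptably now: those in the month of a dose given on the 1st, those in the month after the dose, and those that truly began before the dose in its month. The clearest loss is for the Day 180 booster, whose misplaced AEs appear in no 28-day table. The trial is descriptive, so no test or sample size is affected. The correction is inexpensive and worth making before the by-dose tables are produced.

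**What to change.** In SAP 10.3, add a branch for AE start dates. When only the day is missing and the known month and year contain one or more doses, set the start to the date of the latest dose in that month, unless the recorded stop date is earlier or the record shows onset before that dose. Otherwise keep the current rule. State in SAP 10.5.3 that the imputed date decides dose attribution.

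Do not extend this to AEs with the month also missing, where it would be too blunt. Query those; if unresolved, leave them out of dose-specific attribution or show them separately.

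The cost is SAP wording and one derivation, with no new data. The downside should be named in the SAP: some day-missing AEs that began earlier in the month, before the dose, will move to the later dose (about half of day-missing dose 1 AEs under uniform onset, about 20% under early onset). If any such AEs occur, show the by-dose unsolicited AE tables under both conventions.

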9.1 Safety Assessments

9.1.1 Adverse Events

Definitions of AEs/SAEs, procedures for recording, evaluating, follow-up, and reporting of AEs/SAEs/pregnancy/overdose, as well as assessments of intensity and causality of AEs, are provided in Appendix 10.

Unscheduled visits will be performed when deemed necessary for safety assessments or to ensure data integrity.

Subjects with any Grade 3 solicited or unsolicited AEs reported electronically by the subject will be contacted by the Investigator, and subjects who did not enter any diary information will be prompted and then contacted in case of non-response within 24 hours.

9.1.1.1 **Solicited Adverse Events**

Solicited local AEs (injection site pain, redness, swelling, and itching) and solicited systemic AEs (fever, headache, fatigue, chills, myalgia, arthralgia, nausea/vomiting, and diarrhea) will be recorded on the day of vaccination and the following 7 days using a diary (electronic or paper).

Temperature should be measured orally.

Solicited AEs will be assessed on an intensity scale of absent, mild, moderate, and severe (Table 3 and Table 4). In case of related Grade 3 solicited or unsolicited AEs reported for more than 1 day in the diary, the subject will be questioned to establish the total duration of the AE as exactly as possible and this information will be recorded in the eCRF.

Solicited systemic Grade 3 AEs and unsolicited Grade 3 AEs, except for solicited injection site reactions, must be reported to the medical monitor without delay, on the same day of awareness by the site.

By definition, all local solicited AEs are considered related to trial vaccination. For solicited systemic AEs, the Investigator will assess the relationship between trial vaccine and each occurrence of each AE.

Table 3 Intensity Grading for Solicited Local Adverse Events

AE	Grade	Definition
Pain at injection site	0	Absent
	1	Does not interfere with activity
	2	Interferes with activity and/or repeated use of non-narcotic pain reliever >24 hours
	3	Prevents daily activity and/or repeated use of narcotic pain reliever
Redness	0	<2.5 cm
	1	2.5 – 5 cm
	2	5.1 – 10 cm
	3	>10 cm
Swelling	0	<2.5 cm
	1	2.5 – 5 cm and does not interfere with activity
	2	5.1 – 10 cm or interferes with activity
	3	>10 cm or prevents daily activity
Itching	0	Absent
	1	Mild, no interference with activity
	2	Moderate, some interference with activity
	3	Significant, prevents activity

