9.1.1.2 Unsolicited Adverse Events and Serious Adverse Events

Diaries will also be used for collection of unsolicited AEs on each vaccination day and the following 28 days. In addition, subjects will receive a prompt (by e.g., a phone call or text message) to verify whether the subjects had any health concerns since the last visit.

The occurrence of AEs (serious and non-serious) will be assessed by non-directive questioning of the subject at each visit. AEs volunteered by the subject during or between visits in the diary or detected through observation, physical examination, laboratory test, or other assessments during the entire trial, will be recorded in the eCRF, if they fall within

the reporting period. Subjects should be instructed to report immediately any AEs with serious symptoms, subjective complaints or objective changes in their well-being to the Investigator or the site personnel, regardless of the perceived relationship between the event and the trial vaccine.

The Investigator will assess the relationship between trial vaccine and each occurrence of each AE/SAE.

SAEs and AEs leading to vaccine withdrawal or trial discontinuation will be collected throughout the trial. Non-serious intercurrent medical conditions that may affect the immune response to vaccination will also be collected throughout the trial.

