10.3.6 Missing Data

Analysis of vaccination variables will be done on a valid case basis, i.e., for missing observations, no imputation for missing data, such as last observation carried forward, will be applied. For nCoV spike protein antibodies, concentration values marked as below the lower limit of quantification (LLOQ) will be set to 0.5*LLOQ.

Due to the exploratory design of the trial, no imputation of missing values will be done for any analysis (except the imputation for missing partial dates of AEs and concomitant medication). Reasons for discontinuation from the trial or trial vaccination will be listed and summarized.

Currently no replacement for drop-out subjects is foreseen.

For safety data, some missing or partially missing variables will be imputed as follows:

For start date:

- If the AE start date year value is missing, the date uncertainty is too high to impute a rational date. Therefore, if the AE year value is missing, the imputed AE start date is set to missing.
- If the AE start date year value is less than the vaccination start date year value, the AE started before the vaccination. Therefore:
 - If the AE year is lower than the vaccination year and the AE month is missing, the imputed AE start date is set to the mid-year point (i.e., 01JULYYYY).
 - If the AE year is lower than the vaccination year and the AE month is not missing, the imputed AE start date is set to the mid-month point (i.e., 15MONYYYY).
- If the AE start date year value is greater than the vaccination start date year value, the AE started after vaccination. Therefore, if the AE year is greater than the vaccination year and the AE month is missing, the imputed AE start date is set to the year start point (i.e., 01JANYYYY).

For resolution date:

- If date of resolution is completely missing, it is assumed that it resolved at the date of the end of the AE assessment period.
- If year is present, it is assumed that it resolved on 31 December of that year (i.e., 31DECYYYY), or at the end of the AE assessment period if earlier.
- If year and month are present, it is assumed that it resolved on the last day of that month, or at the end of the AE assessment period if earlier.

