### 9.4 Estimands

ENDPOINTS (subject level)	ESTIMANDS (population level)
Primary Safety	

The frequencies, intensities, and duration of solicited local AEs on Day 1 and Day 29 and the following 7 days by dose and group.
 
The frequencies, intensities, duration, and relationship to trial vaccination of solicited systemic AEs on Day 1 and Day 29 and the following 7 days by dose and group.
 
The occurrence, intensity and relationship to trial vaccination of unsolicited AEs on each vaccination day and the following 28 days by dose and group.
 
The occurrence and relationship to trial vaccination of SAEs and AESIs throughout the trial.
	
Safety set. Subjects who were unblinded and/or received an authorized/licensed COVID-19 vaccine will be censored at the day after unblinding and/or vaccination receipt.
 
The number and percentage of subjects overall and by dose level:
 
Each solicited local AE within 7 days after each trial vaccination by intensity and overall.
 
Each solicited systemic AE within 7 days after each trial vaccination by intensity, by relationship to trial vaccine and overall.
 
The mean duration in days by group with standard deviation of solicited AEs (within the solicited period, total duration).
 
At least 1 unsolicited AEs, at least 1 grade unsolicited AEs and each unsolicited AEs by SOC/PT occurring within 28 days after each trial vaccination and overall by causal relationship to trial vaccine and overall.
 
At least 1 SAE, or at least 1 AESI to vaccine overall by causal relationship to trial vaccine and overall.

ENDPOINTS (subject level)	ESTIMANDS (population level)
Primary Immunogenicity	

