#### 10.5.7 Duration Solicited Adverse Events

Duration of solicited local and systemic adverse events are defined as the sum consecutive days with local/systemic adverse events (days 1 to 8) for the same grade. For example, fatigue with grade 1 occurring on day 2 and 3 and day 7 will be counted as two separate events with the duration 2 days and 1 day. For the duration of solicited local and systemic AEs ongoing beyond Day 8 the following definition is used:

If the AE is present on day 8 in the diary and the same AE is present on day 9 on the eCRF, the sum of days between the date of day 9 and end date for the AE on the eCRF is added to the consecutive days as collected on the diary. If the duration of any AE continues after the next dose and the subject experiences an AE of the same type after the second dose, or booster dose, these two events will be presented separately.

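### SAP 10.3 closes an AE with no resolution date at the end of the trial, not at the end of the AE assessment period as in the protocol, so one lost stop date can add a reaction of about a year to the total-duration mean and SD.

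*SAP*

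**What the plan says.** The two documents give different end points for an AE whose resolution date is unknown.

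- Protocol 10.3.6: "If date of resolution is completely missing, it is assumed that it resolved at the date of the end of the AE assessment period". Year-only and year-month dates are capped at the same point.
- SAP 10.3: "If date of resolution is completely missing, it is assumed that it resolved at the date of the end of the trial". Its rules for partial dates also use the end of the trial as the cap.

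SAP 10.3 introduces its rules with this scope: "For unsolicited AEs, solicited AEs occurring after Day 8 and concomitant medications, some missing or partially missing variables will be imputed as follows". SAP 6.1, which lists changes from the protocol, mentions only cell-mediated immunity and asymptomatic infection.

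The imputed date then feeds the duration of solicited reactions. For a reaction on the diary at Day 8 and on the eCRF at Day 9, SAP 10.5.7 says that "the sum of days between the date of day 9 and end date for the AE on the eCRF is added" to the diary days. No upper limit is given. The primary safety estimand in SAP 9.4 names two versions of the summary: "The mean duration in days by group with standard deviation of solicited AEs (within the solicited period, total duration".

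**The concern.** Duration of solicited local and systemic AEs is part of the primary safety endpoint, and its stated summary is a mean with SD. Both are sensitive to a single extreme value. A mild reaction that faded in its second week, but whose stop date was never captured, would be counted as lasting about a year. The rule does not separate an event known to be ongoing from one whose end is simply unknown.

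SAP 10.3 promises a sensitivity analysis only if missing or partial dates exceed an expectation that is never quantified, and one record is enough to move the mean. A reader of the report could take the resulting figure as evidence of prolonged reactogenicity.

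**Working it through.** **Inputs from the documents**

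- Dose 1 on Day 1, dose 2 on Day 29, last contact on Day 393 with a window of up to +30 days (Protocol Table 1).
- Solicited AEs "will be recorded on the day of vaccination and the following 7 days using a diary" (Protocol 9.1.1): 8 days counting the vaccination day.
- "Diaries will also be used for collection of unsolicited AEs on each vaccination day and the following 28 days" (Protocol 9.1.1.2): 29 days counting the vaccination day.
- Planned sizes (Protocol Table 5): 11 and 12 in the 6 µg groups; at 12 µg, 90 + 200 = 290 per age group and 580 in all; controls, 10 + 20 = 30 per age group. SAP 12.0 presents expansion subjects together with initial-phase subjects.

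**Inputs assumed**, because the documents give neither: the number of durations averaged (n) and the mean of the other durations (m = 2.5 days). Group sizes serve only as reference points for n.

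**Reproducing the plan's own figures**

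- SAP 10.5.7 says that "fatigue with grade 1 occurring on day 2 and 3 and day 7 will be counted as two separate events". Its consecutive-day rule gives 2 days (days 2 and 3) and 1 day (day 7), as the SAP states.
- Protocol 5.5 gives at least 365 days of follow-up after the last primary dose. Day 393 − Day 29 = 364 elapsed days, or 365 counted inclusively.

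**Length of the imputed reaction**, as 8 diary days plus the days from Day 9 after the dose to the imputed end:

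- Dose 1: 8 + (393 − 9) = 392, or 393 inclusively.
- Dose 2: Day 9 after the dose is trial Day 37, so 8 + (393 − 37) = 364, or 365 inclusively.
- At the end of the +30-day window: 423 and 395 inclusively.

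SAP 8.4.4 defines the end of trial by the last subject's last contact. Read literally, earlier enrollees could be assigned longer durations still.

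**Effect of one such record on the mean**: (m(n − 1) + L)/n, with m = 2.5. For n = 290 and L = 393: (722.5 + 393)/290 = 3.85.

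| n | L = 393 (SAP, dose 1) | L = 365 (SAP, dose 2) | L = 29 (28-day cap) | L = 8 (7-day cap) |
|---|---|---|---|---|
| 10 | 41.55 | 38.75 | 5.15 | 3.05 |
| 30 | 15.52 | 14.58 | 3.38 | 2.68 |
| 60 | 9.01 | 8.54 | 2.94 | 2.59 |
| 200 | 4.45 | 4.31 | 2.63 | 2.53 |
| 290 | 3.85 | 3.75 | 2.59 | 2.52 |
| 580 | 3.17 | 3.13 | 2.55 | 2.51 |

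The rise, (L − m)/n, hardly depends on m. For m from 1.5 to 4 days and L = 393 it is about 4.3 days at n = 90 and 0.7 day at n = 580.

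**Effect on the SD**, assuming m = 2 and SD = 1.5 for the other events: one 393-day record raises the SD to about 41 (n = 90), 23 (n = 290) or 16 (n = 580). With a 29-day cap it is 3.2, 2.2 or 1.9.

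**The case against.** **The two rules might coincide.** The protocol never defines the AE assessment period. Protocol Appendix 10 runs AE observation to the end of the trial, though for the period given in Section 9.1.1. SAP 10.5.2 collects solicited events, once the diary closes, with all AEs throughout the trial. On that reading the SAP only spells out a vague term. This stands in part: restoring the protocol wording would not be enough, because the period could be read as 8 days, 29 days or the whole trial. It does not remove the artefact, since on the longest reading the protocol rule would produce it too.

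**Few records are exposed.** A reaction must be on the diary at Day 8, on the eCRF at Day 9, and still lack a stop date after querying. Reactions over by Day 8 are counted from diary days alone. This stands, and the documents give no frequency. Year-month dates also do little harm, because they close at month end.

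**There are other safeguards.** SAP 12.0 presents the median, quartiles and maximum by default and lists the data, SAP 12.8.2 adds by-subject figures, and Protocol 11.4 requires missing data to be queried. An extreme value would probably be seen. But seeing it does not correct the mean and SD that the estimand names. The questioning on total duration in Protocol 9.1.1.1 covers only related Grade 3 events reported for more than one day.

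**Censoring may shorten the durations.** SAP 9.4 and 10.8 censor safety data from the day after unblinding, and all subjects are to be unblinded. The SAP does not say whether this truncates imputed stop dates.

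**A stronger reading is tempting: that the bias falls mainly on CVnCoV.** Nothing in the documents shows how many reactions in either arm run past Day 8. By the arithmetic above, one record moves a control group of 30 much more than a CVnCoV group of 290.

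**Conclusion.** The point holds within limits. The SAP departs from the protocol's wording without declaring it. Followed as written, it turns one unrecovered stop date into a reaction of roughly 365 to 393 days in the total-duration mean and SD. The shift in the mean is about 0.7 day at n = 580 and 1.35 days at n = 290, rising to 6.5 days at n = 60 and more in the 6 µg or control groups. The SD is inflated more severely.

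A reader might infer that the whole primary duration endpoint is compromised. It is not: the within-solicited-period version cannot be affected and the median barely moves. The trial is descriptive, and no stated decision rests on mean duration.

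The size rests on the assumed n and m, on the subject's own Day 393 as the end date, and on censoring not being applied to imputed dates. It also takes the scope of SAP 10.3 to include reactions that began earlier and continue past Day 8. On a narrower reading, SAP 10.5.7 would have no end date for such a record.

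**What to change.** In SAP 10.3, cap imputed AE resolution dates (completely missing, year-only and year-month) at the end of the AE assessment period, and define that period by type of AE. For solicited AEs continuing past Day 8, one option is the vaccination day plus the 28 days already used for AE collection. Keep end-of-trial imputation for concomitant medications and, if the eCRF captures it, for events recorded as ongoing.

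Flag every duration that rests on an imputed stop date. Whenever there is at least one, report the total-duration mean and SD with and without the flagged records, beside the median, in place of the unquantified trigger. State whether censoring at unblinding applies to imputed dates. List any remaining departure from the protocol in SAP 6.1.

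The cost is a short SAP amendment, one flag in the duration dataset and a few table rows, with no effect on trial conduct. The downside is that a truly long reaction with a lost stop date is shortened, which the flag makes visible.
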